### 9.2.10. Actual Treatment

The subjects’ actual treatment will be derived from exposure data. If a subject’s actual treatment is the same as the assigned treatment, then actual treatment is the assigned treatment. If a subject receives a study treatment that is different from the assigned treatment for the entire time of treatment, then actual treatment is the different treatment (the treatment actually received).

### 9.2.11. Treatment Cycle

In order to differentiate cycle variables based on the “assessment” cycle (timeslicing/eCRF collected) versus actual treatment cycle variables based on exposure cycle start dates, treatment cycle, treatment cycle description, day with treatment cycle, day of start within treatment cycle, and day of end within treatment cycle, as appropriate, will be added to adverse events, blood and blood supportive care products, ECG, laboratory, and vital sign analysis datasets.

Treatment cycle:

- For non-planned visits/assessments select the cycle record for each subject where the dataset date variable is greater than or equal to cycle start date and less than or equal to cycle end date.
- For planned visits/assessments where Day 1 assessments are assumed to be done prior to dosing, add 1 to the cycle start date and cycle end date from the cycle dataset. For each subject, select the cycle record where the dataset date variable is

greater than or equal to the cycle start date and less than or equal to the cycle end date.

Treatment cycle description:

- Set treatment cycle description to the cycle dataset cycle description where the cycle dataset cycle is equal to the dataset treatment cycle.

Day within treatment cycle:

- For each subject, dataset date variable minus the cycle start date from the cycle dataset + 1 where the dataset date variable is greater than or equal to the cycle dataset start date and less than or equal to the cycle end date and the cycle dataset cycle is equal to the dataset treatment cycle.

Day of start within treatment cycle:

- For each subject, dataset start date variable minus the cycle start date from the cycle dataset + 1 where the dataset start date variable is greater than or equal to the cycle dataset start date and less than or equal to the cycle end date and the cycle dataset cycle is equal to the dataset treatment cycle.

Day of end within treatment cycle:

- For each subject, dataset end date variable minus the cycle start date from the cycle dataset + 1 where the dataset end date variable is greater than or equal to the cycle dataset start date and less than or equal to the cycle end date and the cycle dataset cycle is equal to the dataset treatment cycle.

### **9.2.12. Extended Loss to Follow-up or Extended Time without an Adequate Assessment**

Since PFS is interval censored, extended loss to follow-up prior to PD or death increases the uncertainty when the event actually occurs. As such, PFS will be analyzed censoring for extended loss to follow-up to account for missed disease assessments prior to disease progression or death.

If 2.5 or more scheduled disease assessments are missed and are then followed by an assessment of PD or death, PFS will be censored at the last adequate assessment prior to PD or death. An adequate assessment is defined as an assessment where the investigator determined response and components of lab and clinical parameters (blood, lymph nodes, organ and constitutional symptoms) are available. The blood laboratory tests in the definition of the “adequate assessment” are haemoglobin, platelets, ANC and lymphocytes.

If the PFS event occurred after the 1st visit up to 2 years (on-treatment or on-study period) where scheduled disease assessments are planned every 8 weeks, a 2.5 assessment window of 140 days (8 weeks + 8 weeks + 4 weeks window) will be used to determine whether there was an extended time without adequate assessment. That is, if the time

difference between PD/death and last adequate assessment is more than 140 days, then PFS will be censored at the last adequate assessment prior to PD/death.

If the PFS event occurred during the follow-up where visits are planned every 3 months for 5 years, then as 2.5 assessment window of 210 days (3 months + 3 months + 1.5 months = 7.5 months = 30 weeks) will be used to determine whether there was an extended time without adequate assessment. This is, if the time difference between PD/death and the last adequate assessment is more than 210 days, then PFS will be censored at the last adequate assessment prior to PD/death.

The following is further explanation regarding the definition of extended lost-to-follow-up:

- 2.5 Assessment windows from last adequate assessment (prior to PFS Event assessment) to PFS Event.
  - If PFS Event occurred during – On-Study planned visits –
    - Visits are planned every 8 weeks after the 1st visit up to 2 years.
    - Window = 8 weeks + 8 weeks + 4 weeks = 20 weeks = **140 Days**.
  - If PFS Event occurred during - During Follow-Up planned visits
    - Visits are planned every 3 months for 5 years.
    - Window = 3 months + 3 months + 1.5 months = 7.5 months = 30 weeks = **210 days**.
  - Truncated time periods
    - First Follow-Up Assessment (3M FU) = **168 days**.
    - Second Follow-Up Assessment (6M FU) = **196 days**.
  - No Last Adequate Assessment is Present
    - **TTE > 140** where TTE = PFS event date – Randomization date + 1
    - Will determine lost to follow-up

### 9.2.13. Date Associated with Response

For each disease assessment after baseline, determine a date associated with the response. For complete response (CR) and partial response (PR), assign to the latest date within the disease assessments. For progressive disease (PD), assign to the earliest assessment date associated with the progression.

### 9.2.14. Derived and Transformed Variables

See Section 11 for details on analyses for time to event endpoints including progression-free survival, time to next treatment, and overall survival, including censoring rules.

### Deriving and Summarizing Pharmacokinetic Parameters

See Section 14 for derivation of PK parameters.

For the purposes of calculating summary statistics and for statistical analysis, all pharmacokinetic parameters with the exception of  $t_{max}$  will be  $\log_e$  transformed.

Between-subject coefficient of variation (CVb%) will be calculated by the following methods, where SD is the standard deviation of the pharmacokinetic parameter data, calculated using either the raw data (untransformed) or the natural logarithm of the raw data (transformed):

Untransformed data:  $100 * (SD/Mean)$

Transformed data:  $100 * (\text{square root}[\exp(SD^2)-1])$

### **Stratification and Prognostic Factors**

In all efficacy analyses, the tests will be stratified by the baseline stratification factors: (1) CR or PR at study entry, (2) number of previous induction treatments (2 vs 3) and (3) type of prior treatment: chemoimmunotherapy, only alkylating monotherapy, or other treatment. The demographic summaries will document the number of subjects who fall into each stratum. PFS, the primary endpoint, will also be summarized according to the stratification factors. Note that it may be necessary to create an additional strata for subjects who received 1 or >3 previous induction treatments.

Subjects will be considered to fall into the respective stratification categories according to the actual data given in the eCRF. Hence, if any misallocations took place in the stratification, it will be the actual data which will be used to determine the stratification of the subject rather than the data as recorded on RAMOS.

In addition to stratification factors, treatment arm as well as age (<70 vs ≥70), gender, race, RAI stage at screening, Binet stage at screening, ECOG (0-1 vs 2), baseline cytogenetics, cytogenetics at relapse, MRD status as well as Ctau and Cmax at Cycle 1 Day 1, Cycle 1 Day 8, and Cycle 4 may be considered as covariates in the Cox regression model to assess the effect of ofatumumab maintenance treatment vs. no further treatment.

The following is a list of the stratification and possible prognostic variables

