6.6. Pharmacokinetics

Blood samples will be collected from subjects receiving ofatumumab predose and 0.5 h after the end of the infusion (EOI) at treatment on Month 1 Week1 (Day 1), Month 1 Week 2 (Day 8), Months 3, 7, 13, 19 and 25. In addition, predose samples will be collected prior to ofatumumab administration on Months 5 and 9. A pharmacokinetic sample (and a HAHA sample) should also be obtained at the last treatment visit if it does not occur at a scheduled sampling time (e.g., if treatment is discontinued early). Samples will also be collected at any time of day during clinic visits at 3 and 6 months post-last ofatumumab dose. Table 5 provides the pharmacokinetic sample collection schedule.

Predose samples may be collected at any time prior to dosing, and 0.5 h post-EOI samples may be collected within a \pm 15 minute window around the scheduled time. The actual date and time of each sample collection will be recorded in the eCRF.

Table 5 Ofatumumab pharmacokinetic sample collection schedule

Month	Week	Visit	Sampling time
1	1	1	Predose, 0.5 h post-EOI
1	2	2	Predose, 0.5 h post-EOI
3	9	3	Predose, 0.5 h post-EOI
5		4	Predose
7		5	Predose, 0.5 h post-EOI
9		6	Predose
13		8	Predose, 0.5 h post-EOI
19		11	Predose, 0.5 h post-EOI
25		14	Predose, 0.5 h post-EOI
28		15	3 months after last dose ^{1,2}
31		16	6 months after last dose ^{1,2}

1. Collect sample at any convenient time on study day.

2. Collect sample relative to last dose of ofatumumab regardless of when it occurs

Sample collection, processing, and shipping instructions are provided in the study procedures manual.

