8.3.5.1. Efficacy Analyses

Primary Analysis

The primary endpoint is progression-free-survival which is defined as the time from randomization to the date of disease progression or death due to any cause. The investigator assessment of response will be assessed according to the IWCLL updated NCI-WG CLL criteria [Hallek, 2008].

An interim analysis of the primary endpoint, PFS, will be performed when 2/3 of the total number of events have occurred (187 events). The interim analysis for PFS will be performed by an IDMC utilizing a significance level of 0.001. The interim analysis of PFS will be conducted in the same manner as described for the final analysis, and further details of the interim analysis will be provided in the IDMC Charter.

The final analysis of PFS will be tested based on a two-sided test with a significance level of 0.0498. The survival distributions will be estimated using Kaplan-Meier survival curves and will be compared using a stratified log-rank test.

In addition to the stratified log-rank test based on the Kaplan-Meier procedure, a Cox regression model will be used and will include covariates for treatment, stratification factors, and other baseline data deemed appropriate. Analytical results will include the estimated hazard ratios along with 95% confidence intervals, and associated probabilities for the effect of treatment, stratification factors and the covariates. The hazard ratio for treatment will express the risk of experiencing disease progression or death for ‘ofatumumab’ vs ‘no further treatment’.

Table 7 PFS Assignment

Situation	Date of Progression or Censoring	Outcome
No baseline tumour	Randomization	Censored
Progression documented between scheduled visits	- Date of assessment of new lymph node (if progression is based on new lymph node) - Date of last assessment (if progression is based on increase in sum of measured lymph nodes)	Progressed
No progression (at end of trial)	Date of last assessment of measured lymph nodes	Censored
Treatment discontinuation for undocumented progression	Date of last assessment of measured lymph nodes	Censored
New anticancer treatment started	Date of last assessment of measured lymph nodes	Censored
Death before first assessment	Date of death	Progressed
Death between adequate assessment visits	Date of death	Progressed
Death or progression after more than one missed visit	Date of last assessment of measured lymph nodes	Censored

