## 8.2. Other Strata and Covariates

In all efficacy analyses, the tests will be stratified by the baseline stratification factors: (1) CR or PR at study entry, (2) number of previous induction treatments (2 vs 3) and (3) type of prior treatment : chemoimmunotherapy, only alkylating monotherapy, or other treatment. The demographic summaries will document the number of subjects who fall into each stratum for the ITT population. PFS, the primary endpoint, will also be summarized according to the stratification factors.

Subjects will be considered to fall into the respective stratification categories according to the actual data given in the eCRF. Hence, if any misallocations took place in the stratification, it will be the actual data which will be used to determine the stratification of the subject rather than the data as recorded on RAMOS.

In addition to stratification factors, treatment arm as well as age, gender and race will be considered as covariates in the Cox regression model to assess the effect of ofatumumab maintenance treatment vs. no further treatment.

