#### **Missing Data**

Missing data occurs when any requested data is not provided, leading to blank fields on the collection instrument. This data will be indicated by the use of a “blank” in subject listing displays. Answers such as “Not applicable” and “Not evaluable” are not considered to be missing data and should be displayed as such.

Since the period of follow-up for any subject will be dependent on efficacy and toxicity, the duration of follow-up will vary among subjects. Consequently, there will be no imputation for missing data. Randomized subjects who do not have any response data will be assumed to be non-responders and will be censored at the date associated with the last visit.

For the PFS endpoint, subjects who are alive and have not progressed at the time of analysis will be censored at the date associated with the last visit with an adequate assessment. If a progression event occurs after an extensive lost-to-follow-up time (more than 2.5 assessment windows), the primary analysis will censor those subjects at the last date of their last visit with an adequate assessment even if subsequent information is available regarding progression or date of death.

Subjects with the designation of treatment relationship for adverse events (AE)s and serious adverse events (SAEs) missing will have the worst case assumed to impute the relationship: if relationship to study treatment is missing it will be assumed to be “Yes”.

There will be no other imputation for missing data other than what’s described in Section 9.2 for partial dates and for missing exposure end dates.

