The final analysis of PFS will be based on a two-sided test with a significance level of 0.0498. The survival distributions will be estimated using Kaplan-Meier survival curves and will be compared using a stratified log-rank test. The Pike estimator [Berry, 1991] of the treatment hazard ratios (HR) will be provided, together with the 95% Confidence Interval (CI). The Pike estimator, which is a nonparametric estimator of the HR, has been specifically developed for survival data and is used as a measure of the relative survival experience of two groups. Within the range of values of the ratio of the hazard rates of interest in clinical trials, the Pike estimator is more efficient in terms of mean square error than the Cox proportional hazard method [Bernstein, 1981]

If there are a sufficient number of progressions or deaths, median PFS, first and third quartiles and 95% CI, will be estimated using the Brookmeyer-Crowley method [Brookmeyer, 1982]. A figure and listing of progression-free survival time will also be provided.

A supplementary table showing the details of the number at risk, number of events, and number censored with the event time will also be produced. Estimates of median PFS after 6 months, 1 year and 2 years of exposure (or observation) will also be provided.

In addition to the stratified log-rank test based on the Kaplan-Meier procedure, a Cox regression model using a stepwise procedure will be used and will include covariates for treatment, stratification factors [CR or PR at study entry; number of previous induction treatments; and type of prior treatment (chemoimmunotherapy, only alkylating monotherapy, or other treatment)] and other baseline data deemed appropriate such as age, Binet stage and baseline cytogenetics data. Treatment will remain forced in the model. An entry/removal significance level of 0.05 will be used. Analytical results will include the estimated hazard ratios along with 95% confidence intervals and associated probabilities for the effect of treatment, stratification factors, and the covariates. The hazard ratio for treatment will express the risk of experiencing disease progression or death for ‘ofatumumab maintenance’ vs ‘observation’ (i.e., no further treatment).

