### **14.2. Deriving and Summarizing Pharmacokinetic Parameters**

For subjects in the active treatment group, the pharmacokinetic parameters  $C_{\tau}$  and  $C_{max}$  will be determined directly from the concentration-time data and will be extracted from the dataset by the Programmer. At each visit, the pre-dose sample will correspond to  $C_{\tau}$  and the 0.5 hr after the end of infusion sample will correspond to  $C_{max}$ . For the purpose of summarizing geometric mean  $C_{\tau}$  values, original NQ values will be imputed to half

the BQL (50 ng/mL). In addition, concentrations at 3 and 6 months after last dose will be extracted from the data by the programmer and labelled as C3mos and C6mos.

Other pharmacokinetic parameters will be derived based on the population pharmacokinetic analysis (Section 14.3).

All derived pharmacokinetic parameters will be listed. For each of these parameters, the following summary statistics will be calculated for each study occasion for which pharmacokinetic parameters were calculated: median, minimum, maximum, arithmetic mean, 95% confidence interval for the arithmetic mean, standard deviation, coefficient of variation, geometric mean, 95% confidence interval for the geometric mean, and standard deviation of logarithmically transformed data. All pharmacokinetic parameters will be reported to at least three significant digits, but to no more significant digits than the precision of the original data.

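### SAP 9.2.14 permits drug concentrations and cytogenetics at relapse in the supportive Cox model for the PFS treatment effect, which protocol 8.3.5.1 and SAP 11.1 describe in terms of baseline data

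*SAP*

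**What the plan says.** Three places describe the Cox model that supports the primary PFS test.

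- Protocol 8.3.5.1: "a Cox regression model will be used and will include covariates for treatment, stratification factors, and other baseline data deemed appropriate".
- SAP 11.1, after Table 1: "a Cox regression model using a stepwise procedure will be used", with treatment forced in and an entry/removal level of 0.05. Besides treatment and the stratification factors, it takes "other baseline data deemed appropriate such as age, Binet stage and baseline cytogenetics data".
- SAP 9.2.14, under Stratification and Prognostic Factors: "Ctau and Cmax at Cycle 1 Day 1, Cycle 1 Day 8, and Cycle 4 may be considered as covariates in the Cox regression model". The same sentence lists baseline cytogenetics and, separately, cytogenetics at relapse, as well as MRD status without a timepoint. It gives the model's purpose as assessing the effect of ofatumumab maintenance against no further treatment.

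SAP 8.2 has a shorter list: besides the stratification factors, "treatment arm as well as age, gender and race will be considered as covariates in the Cox regression model". That list is not in conflict with the others.

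Two related places repeat the post-baseline terms. SAP 11.2 (prognostic markers) allows the concentrations and relapse cytogenetics in a PFS model that also contains treatment group. SAP 8.3 names relapse cytogenetics as a possible subgroup.

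**The concern.** A covariate in a model for a randomized treatment effect should be available in both arms and should not be a consequence of treatment or of the outcome. The terms at issue fail this in different ways. A concentration is not measured in observation subjects at all. Relapse cytogenetics is measured mainly because the subject has progressed.

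At stake is the adjusted HR reported beside the primary test. If the permission is used, that HR either cannot be estimated or comes from subjects selected on the outcome. The open list also leaves the covariate set of this model undefined in an open-label trial.

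**Working it through.** **1. Who has a concentration.** Protocol 6.6: "Blood samples will be collected from subjects receiving ofatumumab predose and 0.5 h after the end of the infusion". SAP 14.2 derives Ctau and Cmax for the active treatment group: "At each visit, the pre-dose sample will correspond to" Ctau, and the sample 0.5 h after the infusion to Cmax. No observation-arm subject has either. The Cycle 1 Day 1 Ctau is drawn before any drug is given, so it carries no exposure information and is still missing for the whole observation arm.

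**2. Whether the SAP supplies a value.** SAP 9.1 ends its missing-data text with "There will be no other imputation for missing data other than" the rules in Section 9.2 for partial dates and exposure end dates. There are other imputations: SAP 9.1 for the relationship of adverse events to treatment, 12.7 for a missing baseline laboratory grade, and 14.2 for concentrations below quantification. None gives an observation-arm subject a concentration.

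**3. Consequence for a complete-case fit.** In a complete-case stepwise fit, a subject missing any candidate is dropped before selection starts. Observation-arm subjects kept with any concentration candidate: 0. The treatment HR is then not estimable, even if the candidate would not have been retained at 0.05. This needs no assumed figure beyond complete-case fitting.

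**4. Who has relapse cytogenetics.** Protocol 6.3.3 collects blood for the prognostic factors at baseline if possible and/or upon relapse. In Appendix 1 that row is marked only at screening and at the withdrawal visit. The relapse value is therefore post-randomization and held mainly by subjects with a PFS event. At the interim, events were 187/479 = 39.0% of subjects, or 187/532 = 35.2% if the planned 532 had been randomized. (479 is the number called evaluable in protocol 1.5; the number randomized is not given.)

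**5. Illustrative size at the interim.** Inputs from the documents: 187 events and medians of 29.4 and 15.2 months, hence an exponential HR of 15.2/29.4 = 0.517 (reported: 0.50). Assumptions not in the documents: exponential PFS; 1:1 arms; uniform accrual over 32.5 months (n = 479) or 28.0 months (n = 532), so that the 187th event falls near the end of accrual; 0-20% of events without a sample (deaths); and a share w of censored subjects with a withdrawal sample. The Cox model with treatment is fitted to subjects who have a sample, with 1,000 replicates per setting.

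| Subjects in the fit | HR, n = 479 | two-sided p < 0.05 | HR, n = 532 | two-sided p < 0.05 |
|---|---|---|---|---|
| all | 0.514 | 99.3% | 0.516 | 99.2% |
| sample held, w = 0 | 0.860-0.863 | 15.4-17.4% | 0.879-0.881 | 12.8-13.8% |
| sample held, w = 10% | 0.723-0.741 | 47.0-48.8% | 0.721-0.745 | 47.5-49.1% |
| sample held, w = 20% | 0.652-0.674 | 72.0-74.8% | 0.648-0.674 | 71.3-73.0% |

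The direction is toward 1 in every row; the size depends on w. No figure is offered for the 280-event analysis. The same exponential model with its reported medians gives 16.89/34.17 = 0.494 against a reported HR of 0.55, and it does not fit the roughly 32 months between the cut-offs (19-Jun-2014 and 20-Feb-2017).

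**6. If missing values were kept as a category.** For relapse cytogenetics, the no-sample category would consist largely of subjects without an event, so the covariate would still encode the outcome. For concentrations, it would contain the whole observation arm and would compete with the treatment term.

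**The case against.** The strongest reply is that the SAP already settles the matter. Section 9.2.14 opens by referring to Section 11 for time-to-event analyses. Section 10.3 speaks of baseline covariates in the Cox models. The coded variable list after the sentence has no concentration and no separate relapse-cytogenetics variable. The sentence itself only permits. This softens the conflict but does not withdraw the sentence. The coded list also omits ECOG, which the sentence names, so it is not exhaustive. And SAP 11.2 repeats the same terms for another two-arm PFS model.

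Second, no passage prescribes complete-case deletion. That is correct. The list of interim outputs in the 280-event SAP shows overall survival figures by IgVH status both with and without missing values. The simulated HRs therefore apply only to a complete-case fit. Keeping a missing category would not make either term a valid covariate.

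Third, the work is done. The final SAP says that the 280-event PFS analysis has been performed and will not be updated, and its output list has no PFS Cox table. The 280-event SAP had already dropped the marker model (Table 2.2080) and PFS by relapse cytogenetics (Table 2.0183), and called its results descriptive. This stands. A reader might take Table 2.0020 as still to be produced; it is not, so the remedy is mainly disclosure.

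SAP Section 15 is not visible and may already hold an exposure-response plan.

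**Conclusion.** The inconsistency is real and confined to a supportive model. SAP 9.2.14 permits terms that do not fit the baseline-data description in protocol 8.3.5.1 and SAP 11.1. With a concentration candidate and complete-case fitting, the treatment HR cannot be estimated; this rests on the sampling plan alone. With relapse cytogenetics and complete-case fitting, the HR moves toward 1 by an amount that depends on assumptions outside the documents.

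Two stronger inferences are not supported. A reader might conclude that the reported HRs of 0.50 and 0.55 are distorted. The documents do not say that either came from a model with these terms, and SAP 11.1 names the Pike estimator for the HR reported with the log-rank test. A reader might also take Table 2.0183 as proof that relapse cytogenetics entered the Cox model. It is a Kaplan-Meier summary and shows only that relapse cytogenetics was used to group PFS at the interim. The stratified log-rank test, the Pike HR, alpha and the 280-event target are not touched. The correction should be made, but it does not bear on the primary conclusion.

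**What to change.** - In SAP 9.2.14, delete Ctau, Cmax and cytogenetics at relapse from the Cox covariate list, and specify MRD status as baseline MRD status, as in the PFS subgroup text of SAP 11.1.
- In SAP 11.2, remove the same post-baseline terms from the two-arm PFS marker model.
- In SAP 8.3, remove relapse cytogenetics as a PFS subgroup, or label that output as descriptive and conditional on relapse.
- Keep any concentration-response analysis within the ofatumumab arm.
- State in the study report which covariates were offered to and retained in Table 2.0020 at the interim and at 280 events. If any was post-baseline, refit with treatment, stratification factors and baseline covariates only.

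The cost is SAP wording, one statement in the report and at most a refit on existing data. No new data are needed, and the primary analysis does not change.
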